10.4 Subgroup analyses

No subgroup analyses will be performed.

10.5 Adjusted analysis

F-CUSToS Protocol Version Number 2.0; Dated 30 January 2025

As outlined above, risk adjustment for baseline value of CPOi (at admission to ICU) will be used in the linear regression for difference in CPOi between admission to ICU and 6 hours post-transplant. All linear and logistic regression models will be adjusted for confounders of interest and presented alongside single comparison tests, such as Fisher's exact test without adjustment.

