3.2 Secondary objectives

Secondary Objective 1:

To compare the effect of Custodiol-HTK solution and St Thomas' solution on the outcomes of cardiac transplantation from donation after brainstem death (DBD) donors.

Hypothesis 1:

There will be a difference between the two solutions in terms of primary graft dysfunction and 30-day mortality.

Secondary Objective 2:

To investigate the effects of Custodiol-HTK solution on the transplanted heart in terms of haemodynamic performance.

Hypothesis 2:

There will be a difference between the two preservation methods in terms of haemodynamic performance, specifically cardiac power output index in the first 6 hours after transplant.

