3.3.3 Exploratory endpoints

Cardiac Power Output Index (CPOi) at admission to ICU post-transplant implantation and at 6h post-operation will be recorded. The difference between CPOi within individuals at admission to ICU and 6h post-operation will be calculated. Cardiac Power Output is defined as the hydraulic energy created by the ventricles per unit time. It is the product of Cardiac Output (CO), measured by Swan Ganz, and the Mean Arterial Pressure (MAP), taking into account the filling state of the individual and indexed to body size. It has been validated as a measure of pump failure in patients with cardiogenic shock. Primary graft dysfunction is effectively the failure of the cardiac allograft to generate sufficient cardiac output and therefore it has been hypothesised that low cardiac power output after transplantation will correspond to the development of PGD and the requirement for mechanical circulatory support. CPOi on admission to ICU has been shown to be correlated with donor to recipient heart mass ratio and inversely correlated to cardiopulmonary bypass time. Previous work from Birmingham has determined a rule-in, rule-out algorithm for cardiac power index as a predictor of severe PGD and early mortality.

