7.3 The randomisation scheme

Randomisation of hearts will occur after consent of the recipient has been secured and after the heart has been deemed acceptable by the medical team. Permuted blocks will be used to randomise each heart to one of the two treatments while ensuring a 1:1 overall allocation ratio. The randomisation will be performed using the secure online platform SealedEnvelope (Sealed Envelope Ltd. 2022. Simple randomisation service. [Online] Available from: https://www.sealedenvelope.com/simple-randomiser/v1/ [Accessed 25 May 2023]). Once consent to participate in the study has been confirmed on the part of the recipient and the suitability of the heart for transplant has been confirmed, the PI, or delegated individual at the transplant recipient centre, will access SealedEnvelope, via a secure and traceable login and generate a random allocation, which will be sent via email to the randomiser and the trial manager. Please note that the randomisation procedure should not be conducted until the intention to proceed with cardiac donation to the named recipient has been confirmed. This should be after the retrieval operation has begun and the retrieval team have assessed the heart in situ and confirmed its suitability for transplant. It is routine for the recipient transplant coordinator to be contacted via telephone during the retrieval operation once suitability to transplant has been confirmed and therefore the randomisation should occur at this stage. This will not delay the retrieval operation. The retrieval team must include the instructions for delivery of both solutions at the WHO pre-operative briefing. It will be the randomiser's responsibility to inform the NORS team of the outcome of the randomisation in a timely manner, via telephone.

Each NORS team will maintain both treatments, and the equipment required to use either treatment, at all times and take both treatments with them to the retrieval centre. Once they have been informed of the treatment allocation, they will prepare and administer the treatment in accordance with the methods set out in this Protocol. Refer to the trial's 'Registration and Randomisation Guidelines for Sites' for more information.

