the individual(s) designated by the PI should input this information into the database. This should be done within 48 hours of written evidence of informed consent being filed in the site file. When a potential participant is called to hospital to receive their transplant, their ongoing consent to take part in the study must be confirmed by a designated individual in that centre. Where consent is withdrawn at this stage this should be recorded by completing the withdrawal of consent form.

Donor baseline data: The donor baseline data outlined in section 7.6.1 will be accessed from the NHSBT transplant registry. This is to avoid duplication of data collection.

Randomisation: The randomisation procedure is outlined in section 7.3 of this Protocol. The outcome of randomisation should be recorded in the CRF, by the delegated individual(s) at the recipient centre.

Organ donation: The organ donation procedure will be carried out in accordance with the UK NORS Protocol. The only change to this Protocol will be the trial treatment, as outlined in section 8 of this Protocol. The outcome of organ donation and the treatment applied should be recorded in the CRF, by the delegated individual(s) at the recipient centre.

Transplant procedure: The transplant implantation procedure will proceed according to the method chosen by the implanting surgeon. There will be no adjustments necessary as a result of taking part in this trial. Operative data will be obtained from the NHSBT Transplant registry and will not need to be recorded in the CRF.

Initial outcome data collection: The delegated individual(s) in the recipient centre should input the CPOi, echocardiogram and PGD data to the database no later than 72 hours after the transplant procedure. This should be conducted in accordance with the blinding instructions laid out in section 7.4 of this Protocol.

CPOi is a calculated variable and will be obtained by uploading the following variables to the database:

- i. Cardiac Output (L/min) measured by Swan-Ganz, using the thermodilution method and taking the average of three measurements, performed as soon as possible, and not later than 1 hour, after admission to ICU.
- ii. Cardiac Output (L/min) measured by Swan-Ganz, using the thermodilution method and taking the average of three measurements, performed 6 hours +/- 2 hours after admission to ICU

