 - ix. History of Liver disease, a categorical variable with categories yes/no, reported as proportions
 - x. History Diabetes mellitus, a categorical variable with categories yes/no, reported as proportions
 - xi. Insulin use, a categorical variable with categories yes/no, reported as proportions
- xii. Renal function (serum creatinine), a continuous variable with serum creatinine at time of donation in milligrams per decilitre (mg/dL) reported as mean
- xiii. Liver function (bilirubin), a continuous variable measured on serum sample at the time of donation in milligrams per decilitre (mg/dL) and reported as mean
- xiv. History of Infection from any source during admission, treated with antibiotics, a categorical variable with categories yes/no, reported as proportions
- xv. History of Malignancy, a categorical variable with categories yes/no, reported as proportions
- xvi. Left Ventricular Ejection Fraction, a continuous variable measured on the echocardiogram closest to the time of donation and given as a percentage, reported as means
- xvii. Ischaemic time, a continuous variable measured in minutes, reported as medians
- xviii. Current or past smoker, a categorical variable with categories yes/no, reported as proportions
- xix. History of Drug abuse, a categorical variable with categories yes/no, reported as proportions

vx. Vasoactive Inotrope score (VIS), a continuous variable calculated as VIS = dopamine (×1) + dobutamine (×1) + amrinone (×1) + milrinone (×15) + adrenaline (×100) + noradrenaline (×100), with each drug dosed in $\mu g/kg/min$. using the maximum dosing rates of vasoactive and inotropic medications ($\mu g/kg^{-1} min^{-1}$) or IU $kg^{-1} min^{-1}$) in the 24 h prior to organ donation, reported as medians

The following baseline data will be collected for all eligible recipients:

- i. Approach to consent, a categorical variable with categories yes/no, reported a proportions
- ii. age, a continuous variable, which will be reported as mean age at time of donation
- iii. sex, a categorical variable, which will be reported as proportions of male, female or other
- iv. ethnicity, a categorical variable, which will be reported as proportions of each category, with the categories being:
 - a) Asian or Asian British
 - Indian
 - Pakistani
 - Bangladeshi
 - Chinese
 - Any other Asian background
 - b) Black, Black British, Caribbean or African
 - Caribbean
 - African
 - Any other Black, Black British, or Caribbean background

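### Section 10.5 adjusts the CPOi change for ICU-admission CPOi as a baseline, but that reading follows the randomised treatment and is itself an outcome, so a between-solution coefficient is not the solution's effect on CPOi

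*Protocol*

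**What the plan says.** **The model.** Section 10.5 says that "risk adjustment for baseline value of CPOi (at admission to ICU) will be used in the linear regression for difference in CPOi" between ICU admission and 6 hours. It introduces this as something already described, but section 10.3 describes no CPOi regression, so 10.5 is the only place where one is specified.

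**Timing of treatment.** On when to randomise, section 7.3 says: "This should be after the retrieval operation has begun and the retrieval team have assessed the heart in situ". Sections 8.6.1 and 8.6.2 have the allocated solution perfused into the donor aortic root after cross-clamping, before storage and implantation.

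**Timing of CPOi.** Section 3.3.3 says: "Cardiac Power Output Index (CPOi) at admission to ICU post-transplant implantation and at 6h post-operation will be recorded". Section 7.7 gives the windows: the first cardiac output is "performed as soon as possible, and not later than 1 hour, after admission to ICU", and the second is "performed 6 hours +/- 2 hours after admission to ICU".

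**Purpose.** Hypothesis 2 in section 3.2 expects the preservation methods to differ in haemodynamic performance, "specifically cardiac power output index in the first 6 hours after transplant". The endpoint table in section 3.3.4 lists both readings as outcome timepoints. It plans absolute differences between solutions and between PGD groups, as well as change over time.

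**The concern.** A baseline covariate in a randomised comparison has to be fixed before allocation, so that treatment cannot have altered it. Admission CPOi fails this test. The graft has been arrested, stored and reperfused under the allocated solution by the time it is measured, and the reading falls within the period that Hypothesis 2 is about.

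If the solution changes graft function at admission, adjusting for that reading takes out part of the effect under study. The remaining coefficient cannot safely be read as an effect on later recovery either. Section 3.3.3 notes that admission CPOi is related to donor-to-recipient heart mass ratio and bypass time. If such factors also influence 6-hour CPOi, comparing arms at equal admission CPOi can disturb the balance that randomisation gave them.

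At stake is what the CPOi regression would be taken to show about the two solutions, and whether the same model passes into the efficacy trial.

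**Working it through.** **Inputs.** The order of events comes from sections 7.3, 8.6, 3.3.3 and 7.7: randomisation, perfusion, implantation, admission CPOi, 6-hour CPOi. The protocol gives no CPOi effect, SD, correlation or power, so it has no figure of its own to reproduce. All numerical values below are assumptions shown over a range.

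**Formula.** Let d0 and d6 be the between-solution differences at admission and at 6 hours in SD units, with equal SDs and within-arm correlation ρ.

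- The unadjusted change (6 h minus admission) estimates d6 − d0.
- The within-arm slope of the change on admission CPOi is ρ − 1.
- The adjusted treatment coefficient is therefore (d6 − d0) − (ρ − 1)·d0 = d6 − ρ·d0. Regressing 6-hour CPOi on arm and admission CPOi gives the same coefficient.
- The share of the 6-hour effect lost is ρ·d0/d6.

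**Share of the 6-hour effect lost.**

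| Admission effect | ρ = 0.3 | ρ = 0.5 | ρ = 0.7 | ρ = 0.9 |
|---|---|---|---|---|
| d0 = 0 | 0% | 0% | 0% | 0% |
| d0 = d6/2 | 15% | 25% | 35% | 45% |
| d0 = d6 | 30% | 50% | 70% | 90% |
| d0 = 2·d6 | 60% | 100% | 140% | 180% |

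Above 100% the coefficient has the wrong sign. This happens when ρ·d0 exceeds d6.

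**Check by simulation** (400,000 patients per scenario). With d0 = d6 = 0.5 and ρ = 0.7, the formula gives 0.15 and the simulation 0.147. With d0 = 0.5, d6 = 0.25 and ρ = 0.7, they give −0.10 and −0.102.

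**Change score alone.** With d0 = d6, the unadjusted change has expectation 0 whatever the size of the effect. Dropping the covariate and keeping the change score is therefore not a remedy.

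**Power illustration** (assumed 0.8 SD at both times, all 50 hearts with CPOi at 25 per arm, two-sided 5%, normal approximation). The unadjusted 6-hour comparison has z = 0.8/√(2/25) = 2.83, so power is about 0.81. The adjusted model has effect 0.8(1 − ρ) and residual SD √(1 − ρ²). Its power is 0.55, 0.37, 0.22 and 0.10 for ρ = 0.3, 0.5, 0.7 and 0.9. These adjusted figures ignore the variance inflation from the arm–covariate correlation, a factor of 1 + 0.8²/4 = 1.16, so they are if anything slightly high.

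**The case against.** **The total effect is still estimated elsewhere.** Section 3.3.4 plans absolute differences between solutions at both times, section 10.3.3 provides unadjusted Welch tests, and section 10.5 presents adjusted models beside unadjusted tests. A benefit that is constant over time would show there. This stands and limits the damage. It does not correct the one CPOi regression that the protocol specifies.

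**The model's literal outcome is the change.** Measured against d6 − d0, the covariate removes nothing: with equal effects the change has expectation 0 and the adjusted coefficient is (1 − ρ)·d6. This also stands. The change score and the covariate are at fault together.

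**Section 10.5 does not name the exposure.** The exploratory objective also compares patients with and without PGD, and adjusting for admission CPOi in that model breaks no randomised comparison. The point is therefore confined to between-solution models, which Hypothesis 2 makes the natural reading.

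**Ischaemic time.** A reader might infer that the same error extends to it. Section 10.3.1 lists it among donor baseline data ("Ischaemic time, a continuous variable measured in minutes, reported as medians"), section 1 describes it as starting with delivery of the solution, and section 10.5 says "All linear and logistic regression models will be adjusted for confounders of interest". But no section names ischaemic time as a covariate. Its listing is for description, and the choice of confounders is a matter for the SAP. The documents do not support a finding on it.

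**Conclusion.** The protocol labels a post-treatment outcome as a baseline and adjusts for it. In a between-solution comparison with equal SDs, the model estimates d6 − ρ·d0 and not the solution's effect on CPOi. That much follows from the protocol's own sequence of events.

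A reader might go further and infer that the model removes most of the effect, or that Hypothesis 2 cannot be answered. The documents support neither reading. The loss depends on ρ and on d0/d6, which are not given. Over the assumed values it runs from 0% to more than 100%, and it exceeds one half only when ρ·d0/d6 is above 0.5. Hypothesis 2 can still be addressed through the absolute comparisons.

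The consequence is modest. Sections 3.3.3 and 7.7 class CPOi as exploratory, although the trial summary and section 3.2 place it under secondary outcomes and objectives. The success rule in section 3.3.1 does not use it. The main reason to correct it is section 4, which says that the design replicates the larger trial except for the primary outcome, so the model could be carried forward.

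**What to change.** - In section 10.5, stop calling admission CPOi a baseline, and do not adjust for it in any between-solution analysis.
- Name the by-arm comparison of CPOi at admission and at 6 hours, already listed in section 3.3.4, as the analysis for Hypothesis 2. Two separate comparisons are enough. One repeated-measures model with arm, time and their interaction is an alternative.
- Limit covariates in these models to variables fixed before randomisation, for example the pre-operative haemodynamics in section 7.6.2.
- Keep the within-patient change as a descriptive summary.
- State in section 10.5 which exposure each CPOi model concerns, solution or PGD group, and remove or complete the reference to an earlier description.

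The cost is wording in the protocol and SAP. No new data are needed.

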10.6 Interim analysis and criteria for the premature termination of the trial

Interim analysis will not routinely be performed. If interim analysis is requested by the Data Safety and Monitoring Committee then this will be performed by the DSMC's independent statistician.

10.7 Participant population

The primary outcome will be analysed on an intention to treat basis. Secondary outcomes will be analysed "as randomised".

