3.3.2 Secondary endpoints

- i. The proportion of eligible recipients who consent to take part in the study.
- ii. The proportion of eligible donor cardiac allografts where randomisation occurs according to the Protocol.
- iii. The proportion of eligible donor cardiac allografts where the heart is preserved in the correct randomly allocated solution.
- iv. Key outcome completeness
- v. The development of Primary Graft Dysfunction, according to the 2014 ISHLT Consensus Definition(2), within 24 hours of transplant implantation.
- vi. Echocardiographic parameters from trans-oesophageal echo immediately after transplant implantation, including:
 - a. Left Ventricular ejection fraction
 - b. Left ventricular maximal posterior wall thickness
 - c. Maximal septal wall thickness
 - d. Left ventricular function
 - e. Right ventricular function
 - f. The presence/absence of regional wall motion abnormalities
- vii. 30-day all-cause mortality.
- viii. 6-month survival rates, determined at the end of the study.
- ix. Development of the following post-operative complications will be recorded:
 - a. Dysrhythmias (defined by the clinical team) within 30-days of transplant implantation
 - b. Myocardial Infarction (defined according to ESC definitions of myocardial infarction post cardiac surgery) within 30-days of transplant implantation
 - c. Stroke (defined by radiological evidence of ischaemia/haemorrhage and clinical symptoms of stroke) within 30-days of transplant implantation
 - d. Transplant rejection (defined by the clinical team and confirmed on histopathology of biopsy material or post-mortem) within 30-days of transplant implantation
 - e. The need for post-operative renal replacement therapy within 30-days of transplant implantation
 - f. Infection (from any source requiring antibiotic therapy) within 30-days of transplant implantation
 - g. Venous thromboembolism (defined by radiological evidence and need for treatment) within 30-days of transplant implantation
 - h. Re-admission to any UK hospital within 30 days of transplant implantation
 - i. Hyponatraemia within 24 hours of transplant implantation (Na<125mEq/L on any serum laboratory-analysed sample, not blood gas analysis)
- x. Median length of initial ICU stay in hours
- xi. Median length of initial hospital stay in days

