7.9 Qualitative assessments

As this is a feasibility trial, our primary outcome will be determined by numeric proportions and supplemented by qualitative assessments as follows:

Recipient decline to consent: Where an eligible recipient declines to consent to participate, the delegated individual(s) taking informed consent should document the reason for decline to consent, where provided (free text). The potential participant must be informed that they do not need to provide a reason.

Randomisation failure: Where an eligible recipient has provided consent to participate in this study and receives an eligible transplant that has not been randomised, the reason for failure to randomise should be recorded by the delegated individual(s) in the recipient centre.

Treatment allocation failure: Where an eligible recipient has provided consent to participate in this study and receives an eligible transplant that has been randomised but the incorrect treatment has been applied, the reason for the application of the incorrect treatment should be recorded by the delegated individual(s) in the recipient centre.

Blinding: Delegated individual(s) who record data in the CRFs will be asked whether they could have been blinded to the treatment allocation. Data from these questions will be assessed to determine the feasibility of blinding outcome assessors in the larger trial.

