Early cessation would be considered if there was a 30% absolute risk reduction in primary graft dysfunction in one treatment arm, as this is the point at which there would be sufficient power to confidently confirm that one arm reduced primary graft dysfunction with a 5% significance level at 80% power. Early cessation will also be considered where the DSMC has concerns that one treatment leads to a significant increase in SARs and/or SAEs.

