9 PHARMACOVIGILANCE

9.1 Definitions

Term	Definition					
Adverse Event (AE)	Any untoward medical occurrence in a participant to whom a medicinal					
	product has been administered, including occurrences which are not					
	necessarily caused by or related to that product.					
Adverse Reaction	An untoward and unintended response in a participant to an investigational					
(AR)	medicinal product which is related to any dose administered to that					
	participant. The physics "manning to an investigational medicinal product" means that					
	The phrase "response to an investigational medicinal product" means that a causal relationship between a trial medication and an AE is at least a					
	reasonable possibility, i.e., the relationship cannot be ruled out.					
	All cases judged by either the reporting medically qualified professional or					
	the Sponsor as having a reasonable suspected causal relationship to the trial					
	medication qualify as adverse reactions. It is important to note that this is					
	entirely separate to the known side effects listed in the SmPC. It is					
	specifically a temporal relationship between taking the drug, the half-life,					
	and the time of the event or any valid alternative aetiology that would					
	explain the event.					
Serious Adverse Event	A serious adverse event is any untoward medical occurrence that:					
(SAE)	• results in death					
	• is life-threatening					
	requires inpatient hospitalisation or prolongation of existing					
	hospitalisation					
	results in persistent or significant disability/incapacity					
	consists of a congenital anomaly or birth defect					
	Other 'important medical events' may also be considered serious if they					
	jeopardise the participant or require an intervention to prevent one of the					
	above consequences.					
	NOTE: The term "life-threatening" in the definition of "serious" refers to					
	an event in which the participant was at risk of death at the time of the					
	event; it does not refer to an event which hypothetically might have caused					
Serious Adverse	death if it were more severe. An adverse event that is both serious and, in the opinion of the reporting					
Reaction (SAR)	Investigator, believed with reasonable probability to be due to one of the					
Macdon (Dill)	trial treatments, based on the information provided.					
Suspected Unexpected	A serious adverse reaction, the nature and severity of which is not					

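### Section 10.7 analyses every secondary outcome as randomised, with no companion table by solution received for harm-type outcomes such as hyponatraemia

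*Protocol*

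**What the plan says.** Section 10.7 is two sentences long. On the primary outcome: "The primary outcome will be analysed on an intention to treat basis". On the rest: "Secondary outcomes will be analysed" as randomised. No safety or by-solution-received set is defined there or anywhere else in the protocol.

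Section 3.3.2 places the complications inside the secondary endpoints, as item ix: "Development of the following post-operative complications will be recorded". The list covers dysrhythmia, myocardial infarction, stroke, rejection, renal replacement therapy, infection, venous thromboembolism, readmission and hyponatraemia. Hyponatraemia is a serum sodium below 125 mEq/L within 24 hours; the others have a 30-day window.

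Three further places bear on the point:

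- Section 3.3.1 makes preservation in the allocated solution the third component of the primary composite.
- Section 7.9 asks for the reason in any case where the heart "has been randomised but the incorrect treatment has been applied".
- Section 7.7 has the treatment applied recorded in the CRF.

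**The concern.** As randomised is the right basis for comparing the two solutions on PGD, mortality, haemodynamics and echocardiography. It suits a possible harm of a particular solution less well. If a heart allocated to one solution is given the other, an event that follows is counted under the solution the recipient never had. Crossover therefore pulls the two arms together and makes a real difference in harm look smaller, which is the unsafe direction.

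Hyponatraemia is the clearest case. Its 24-hour window matches the period that section 9.2 gives as the longest over which an event could reasonably be tied to the treatment. It is also absent from that section's list of expected transplant complications. The protocol collects what is needed to show events by solution received but does not plan to show them.

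**Working it through.** No figure in the protocol depends on this rule, so there is nothing to reproduce. The check is a reading of the text plus an illustration of size.

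**Inputs from the protocol**
- Rule: as randomised for all secondary outcomes (10.7).
- Outcomes covered: 3.3.2 ix, items a to i.
- Allocation 1:1 (section 4) and 50 hearts (10.1), taken here as 25 per arm.

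**Inputs assumed, because the protocol gives none**
- Crossover fraction c: 0% to 20% in each arm.
- Hyponatraemia risk by solution received: 20% and 4%, for illustration only.
- Hearts that cross over carry the same risk as other hearts given that solution.

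**Formula.** Let a and b be the risks under the two solutions actually given.

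- Arm A as randomised = (1 − c)a + cb
- Arm B as randomised = (1 − c)b + ca
- Difference = (1 − 2c)(a − b)

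At c = 10%, arm A = 0.9 × 20 + 0.1 × 4 = 18.4% and arm B = 0.9 × 4 + 0.1 × 20 = 5.6%. The difference is 12.8 points, against a true 16.0.

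| c per arm | Factor (1 − 2c) | Loss | Arms read | Difference (points) | Expected events under the wrong solution, 25c(0.20 + 0.04) |
|---|---|---|---|---|---|
| 0% | 1.00 | 0% | 20.0% vs 4.0% | 16.0 | 0 |
| 5% | 0.90 | 10% | 19.2% vs 4.8% | 14.4 | 0.3 |
| 10% | 0.80 | 20% | 18.4% vs 5.6% | 12.8 | 0.6 |
| 20% | 0.60 | 40% | 16.8% vs 7.2% | 9.6 | 1.2 |

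If crossover differs between the arms, the factor becomes 1 minus the sum of the two fractions. With 12% in one arm and none in the other, 88% of the difference is kept.

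**Against sampling error.** With 25 per arm, one event moves an arm's rate by 1/25 = 4 points. The standard error of the 20% versus 4% difference is √(0.20 × 0.80/25 + 0.04 × 0.96/25) = √0.007936, about 8.9 points. The loss at c = 10% is 16.0 − 12.8 = 3.2 points, roughly a third of one standard error.

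**The case against.** The strongest reply is that section 10.7 says nothing false. Analysing a randomised comparison as randomised is standard, and an extra table by treatment received is often left to an SAP, which is not shown here. Section 10.7 does not say that no other table may be made. Most of the 3.3.2 ix complications are also comparative clinical outcomes: section 3.3.4 lists them under the objective of comparing the solutions. Analysing them by solution received would give up randomisation in a trial whose surgical teams know the allocation. The numbers are small, no feasibility decision rests on these outcomes, and section 8.13 has each randomised case reviewed for compliance with allocation.

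Most of this stands. It rules out replacing the as-randomised analysis, and it keeps the point minor. It does not remove the point, because the protocol itself fixes a single rule for the whole list, and that rule alone shows a solution-related harm under the wrong label whenever a crossover occurs.

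A reader might also infer more than the text supports:

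- **That adverse reactions are misattributed.** Section 9.1 defines an adverse reaction as a response to a "medicinal product which is related to any dose administered to that" participant. SAEs, SARs and SUSARs are not secondary endpoints. Section 9.3 has causality judged event by event against the trial drug, and section 9.5 does the same for deaths. Section 10.7 does not govern them.
- **That DSMC decisions use mislabelled tables.** Section 7.10 allows early cessation to be considered where "the DSMC has concerns that one treatment leads to a significant increase in SARs and/or SAEs", but nothing says that the DSMC's tables follow 10.7.
- **That the protocol expects crossover.** Section 7.9 is conditional: it says what to record if the wrong solution is given. No rate is predicted.

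**Conclusion.** The point holds in a narrow form. The single as-randomised rule in section 10.7 covers outcomes that double as harm measures, chiefly hyponatraemia. If crossover occurs, those outcomes are counted under the solution not given and the contrast shrinks by (1 − 2c).

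The size depends wholly on a crossover rate that the protocol does not state: nil at zero, 10% at c = 5%, 20% at c = 10%. The factor assumes equal crossover in both arms and no link between crossing over and risk. With about 25 hearts per arm the distortion is well inside sampling error. This is therefore a minor improvement to the plan. It does not undermine the feasibility conclusion, the efficacy comparisons or safety reporting.

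**What to change.** Keep as randomised as the main analysis for every secondary outcome. Add one sentence to section 10.7: hyponatraemia and the other 3.3.2 ix complications will also be tabulated by the solution actually received, using the treatment applied as recorded in the CRF.

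The cost is that sentence and one table from data already collected. The downside is that the by-received table is not fully protected by randomisation, since the reasons for crossing over may be related to risk. It should therefore be shown beside the as-randomised table, labelled descriptive, and not replace it. If no heart crosses over, the two tables are identical and a statement to that effect is enough.
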